**Study Design:**

This is a 3-armed randomized, parallel, controlled, interventional clinical study enrolling 45 patients with myofascial pain originated from masseter muscle.

**Eligibility**

- Inclusion Criteria: Definite diagnosis of myofascial pain with a referral, based on the DC/TMD criteria, presence of the myofascial pain for at least six months; the presence of one or more trigger point in the unilateral or bilateral masseter muscle, no history of any invasive procedures in the related masseter muscle in last two years;
- Exclusion criteria: Factors that can cause pain in the orofacial region other than MTPs (decayed tooth, TMJ internal disorder, etc.), presence of any muscle disorders or neuropathy (e.g. fibromyalgia), patients with a history of hypersensitivity to local anesthetics.

Patients were grouped according to the treatment they received: Masseteric nerve block (MNB), TrP injections with local anesthetic (LA) and dry-needling (DN). Localization of the MTPs was based on the clinician's sense and patients' expressions of pain. Local twitch response was not observable in all cases. This procedure was completed by using digital palpation. Clinical examiner's palpation was calibrated using a pressure algometer (1.5 Kg).

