**Sample size**

The sample size was calculated using IBM SPSS 22 (IBM SPSS Statistics for Windows, Version 22.0. Armonk, NY: IBM Corp.). Based on a power of 0.80 and an alpha value of 0.05, the sample size was calculated to be a total of 45 subjects with 15 in each group.

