**Outcome measures**

The Rate of Pain on Function (PoF) assessed by Numerical pain Scale (NRS): Patients rated their pain on function (pain during chewing or speaking etc.) on a Numeric Rating Scale (NRS) (0–10 where 0 is no pain and 10 is the worst pain imaginable)

The Rate of Pain Intensity on Palpation (PoP): Patients rated their pain intensity on masseter muscle by a 4-point Likert-type scale (0 = no pain, 3 = as worst pain imaginable) while a calibrated examiner palpating their masseter muscle.

The measurement of pain-free maximum mouth opening (MMO) in millimeters.: Pain-free MMO was measured as the distance between the incisal edges of the upper and lower incisors while patient's mouth is open as possible without any assistance and without pain in masseter muscle. Three measurements were performed, and their average is recorded.

The patients were assessed before the injections (T0), and at one week (T1), 4 weeks (T2), and 12 weeks (T3) after the injections. Patient's pain on palpation, pain on function and maximum mouth opening values were reexamined and recorded on follow-up appointments. Treatment protocol and the outcome measures were recorded in the patient's form.

Statistical Analysis Plan: Descriptive statistics of variables were presented as mean  $\pm$  standard deviation for continuous variables and n (%) for categorical variables in statistical analysis. IBM SPSS 22 was used to analyze the data (IBM SPSS Statistics for Windows, Version 22.0. Armonk, NY: IBM Corp.). Pearson chi-square test was used in the analysis of categorical variables. One-way ANOVA was used in the analysis of discontinuous variables (such as % difference Baseline-T1). Bonferroni test was used as post hoc test after ANOVA. Repeated Measures ANOVA test was used when testing group differences for repeated measurements. Bonferroni correction was used in multiple comparisons when determining the differences between the groups at each time point. The statistical significance level was accepted as  $p < 0.05$ .

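### No minimum baseline pain is required for entry, so patients with little pain on function can be enrolled; this can cost sensitivity and makes the planned percent-change analysis unstable

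*Combined protocol and SAP*

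**What the plan says.** The Study Design section describes a randomised three-arm trial "enrolling 45 patients with myofascial pain originated from masseter muscle". Under Eligibility, entry requires "Definite diagnosis of myofascial pain with a referral, based on the DC/TMD criteria", then "presence of the myofascial pain for at least six months; the presence of one or more trigger point in the unilateral or bilateral masseter muscle", and no invasive procedure in that muscle in the last two years. Neither the inclusion nor the exclusion criteria mention a PoF score, a pain-on-palpation (PoP) score or mouth opening.

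Outcome measures lists PoF on a 0–10 scale, PoP on a 0–3 scale and pain-free maximum mouth opening (MMO) in millimetres, all taken at T0, week 1, week 4 and week 12. For PoF, "Patients rated their pain on function (pain during chewing or speaking etc.) on a Numeric Rating Scale (NRS"). Unlike PoP and MMO, this rating is not tied to the masseter.

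The statistical analysis plan, in the same section, uses one-way ANOVA for variables such as the percent difference from baseline to T1, and repeated-measures ANOVA for group differences over time. It names no adjustment for T0 as a covariate. The Sample size section says that "the sample size was calculated to be a total of 45 subjects with 15 in each group".

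**The concern.** Diagnosis and duration show that the condition exists; as written they do not fix how much it hurts on the day of entry. A patient with a tender masseter trigger point and a PoF of 1 or 2 meets every criterion and has little room to improve on PoF.

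Two things are at stake. First, if treatments reduce pain roughly in proportion to its starting level, low-PoF patients contribute a small difference between arms and pull the average contrast down. Secondly, percent change divides by T0: it does not exist at T0 = 0, and at T0 = 1 or 2 a one-point fluctuation becomes a very large percentage. With 15 patients per arm, a few such values can dominate the within-arm variance.

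**Working it through.** **The plan's own figure.** The stated inputs are "Based on a power of 0.80 and an alpha value of 0.05" and 15 per arm. No effect size, SD, outcome or test is given, so 45 cannot be reproduced. Working backwards at two-sided alpha 0.05 (sidedness is my assumption), 45 patients give 80% power for Cohen's f = 0.48 in a three-group one-way ANOVA, or a pairwise difference of 1.06 SD (1.25 SD at Bonferroni alpha 0.05/3). Differences smaller than that already have less than 80% power, so there is little reserve.

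**Absolute change in PoF.** Assumptions, none from the documents: one arm lowers PoF by 60% and another by 30%; most patients enter with mean PoF 6 and a share q with mean PoF 1.5.

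- Contrast at a given T0 = (0.60 − 0.30) × T0, which is 1.8 points at T0 = 6, 0.6 at T0 = 2 and 0.3 at T0 = 1.
- Mixed contrast = 0.3 × [6(1 − q) + 1.5q] = 1.8 × (1 − 0.75q).
- At q = 1/3: 0.3 × (4 + 0.5) = 1.35, and 1.35/1.80 = 0.75.

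Taking 80% power at N = 45 as the start and holding the SD constant (a simplification), ANOVA power becomes:

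| q | Loss of contrast | Power at N = 45 | Total N for 80% |
|---|---|---|---|
| 0 | 0% | 0.80 | 45 |
| 10% | 7.5% | 0.73 | 54 |
| 20% | 15% | 0.65 | 63 |
| 1/3 | 25% | 0.54 | 78 |
| 40% | 30% | 0.48 | 90 |

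**Percent change in PoF.** A one-point change is 1/6 = 17% at T0 = 6, 1/2 = 50% at T0 = 2 and 100% at T0 = 1; at T0 = 0 the ratio is undefined. Under the proportional model the mean contrast stays at 30 percentage points for any T0 above 0. The variance does not stay the same. Assume a noise SD of 1.5 points:

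- SD of percent change at T0 = 6: 1.5/6 = 25 points. At T0 = 1: 1.5/1 = 150 points, before allowing for the ends of the scale.
- All 15 patients at T0 = 6: standardised contrast 30/25 = 1.20.
- One of 15 at T0 = 1: average variance (14 × 625 + 22,500)/15 = 2,083, SD about 46, standardised contrast 30/46 = 0.65.

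A simulation with reductions of 60%, 30% and 30%, T0 about 6, noise SD 1.5 and 15 per arm gives ANOVA power of about 0.86 with no low-PoF patient. With one patient per arm at PoF 1, it falls to about 0.57 on percent change and 0.77 on absolute change. I reran it with the T0 SD between 0 and 1.5, with and without limiting follow-up scores to 0–10. Power started at 0.84–0.92 and fell to 0.47–0.63 on percent change and 0.77–0.85 on absolute change. With T0 as a covariate it was 0.87–0.88.

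**The case against.** The strongest reply is that no document shows that such patients were enrolled. There is no T0 distribution, q could be near 0, and at q = 0 nothing is lost. The entry criteria also do more than name a disease: the DC/TMD diagnosis must be definite, and "Localization of the MTPs was based on the clinician's sense and patients' expressions of pain". That makes a PoP of 0 at entry unlikely. All of this stands. It limits the point to what the criteria permit, and mainly to PoF, since pain expressed on palpation says little about pain on chewing or speaking.

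A second reply is that, under proportional effects, the mean percent-change contrast is not diluted. That is correct for the mean, but it overlooks the variance, which is where the damage arises.

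A third is that admitting the full diagnosed population is a legitimate choice, and that a cut-off on the same rating used as baseline builds in regression to the mean. The first part is a fair preference, but percent change then remains a poor choice of analysis. The second affects improvement within each arm; in a randomised comparison it affects all arms alike.

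A reader might also cite the patient whose functional pain comes mainly from another muscle. That concerns the source of pain, not its severity: such a patient could score high and pass any severity minimum.

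**Conclusion.** The point holds as a gap in the entry criteria that is cheap to close. No minimum T0 score is set, so patients with little functional pain can be enrolled. The likely consequence is lost sensitivity on PoF and an unstable percent-change analysis.

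The size is conditional. The 0.75q loss rests on proportional effects and on assumed mean T0 values of 1.5 and 6. The power figures rest on a constant SD or on the simulation settings given. The division by zero at T0 = 0 needs no assumption.

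A reader might infer that every between-arm difference is diluted. The documents do not support that: MMO has no pain-score floor, PoP probably starts above 0 (though a score of 1 leaves only one step), and the mean percent-change contrast need not shrink. Nor can it be said that low-PoF patients can only stay the same or worsen; that is true only at T0 = 0. Nor is there systematic bias: randomisation spreads such patients evenly on average, leaving only chance imbalance at 15 per arm.

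**What to change.** Add to the inclusion criteria a prespecified minimum T0 PoF score, rated for masseter pain and checked before randomisation. The pre-injection PoF rating already planned can serve. The sponsor should choose and justify the value; the documents support no particular figure. It must be above 0, and a minimum of 1 would cure the undefined ratio but not the instability.

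Eligibility and Outcome measures are written largely in the past tense, so enrolment may be complete. In that case, report the T0 distribution of PoF by arm and analyse follow-up PoF with T0 as a covariate instead of as percent change. This does not restore contrast lost through low-PoF patients, but it removes the division by T0.

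The cost of the criterion is one sentence and no new measurement. Some screened patients are excluded, recruitment is slightly slower, and results apply to patients with at least that level of functional pain. Improvement within each arm will include regression to the mean, so it should not be read as treatment effect; between-arm comparisons are unaffected.

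### The only definition of the comparison groups is by treatment received, so analysis by randomised arm is not assured

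*Combined protocol and SAP*

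**What the plan says.** The Study Design section states: "This is a 3-armed randomized, parallel, controlled, interventional clinical study". The Sample size section plans equal arms: "the sample size was calculated to be a total of 45 subjects with 15 in each group".

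The paragraph after the eligibility criteria then says "Patients were grouped according to the treatment they received" and names the three techniques: masseteric nerve block, trigger-point injection with local anaesthetic, and dry needling. No other sentence says how a patient comes to belong to a group.

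The Statistical Analysis Plan, at the end of Outcome measures, uses the term without defining it: "Repeated Measures ANOVA test was used when testing group differences for repeated measurements". It names no analysis population. It does not say how to count a patient whose treatment differed from the assignment.

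**The concern.** In a randomised trial the arms are comparable because chance decided who went where. That holds for groups formed by assignment. It need not hold for groups formed by what was done, because the reasons for doing something else may be related to the patient's pain, anatomy or preference.

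An analyst who opens the plan to find out what a group is will find one answer, and that answer is treatment received. If even one patient had a technique other than the assigned one, following the text would move that patient's results into another arm. The comparison would then no longer be fully randomised. With small arms, a few such moves could matter.

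**Working it through.** **1. The text, set side by side.**

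| Place | What it settles |
|---|---|
| Study Design | Patients are randomised to three arms |
| Eligibility, grouping sentence | Groups are formed by treatment received |
| Sample size | 15 per group, 45 in total (3 × 15 = 45) |
| Statistical Analysis Plan | Groups are compared; the term is not defined |

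The second row is the only one that can supply a definition to the fourth. Nothing provides for analysis by assigned arm.

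**2. Weight of one patient** (15 per arm, from Sample size).
- Share of the arm left: 1/15 = 6.7%.
- Share of the arm joined, once counted there: 1/16 = 6.25%.

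**3. Shift in the mean of the arm joined.** If *m* patients move in, and their mean outcome differs by *D* points from that arm's own 15 patients, the arm mean shifts by *mD*/(15 + *m*). Both *m* and *D* are assumptions. On the 0–10 pain-on-function scale:

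| | *D* = 1 | *D* = 3 |
|---|---|---|
| *m* = 0 | 0 | 0 |
| *m* = 1 | 1/16 = 0.06 | 3/16 = 0.19 |
| *m* = 2 | 2/17 = 0.12 | 6/17 = 0.35 |
| *m* = 3 | 3/18 = 0.17 | 9/18 = 0.50 |

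**4. Effect on the test, in an assumed extreme case.** 100,000 trials were simulated with no treatment effect, 15 normally distributed outcomes per arm, and a one-way ANOVA at 0.05. The *m* worst outcomes in one arm were counted in a second arm; the third arm was left alone.

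| Moves | Spurious difference between the two arms (SD) | Type I error, as treated | Type I error, as randomised |
|---|---|---|---|
| 0 | 0.00 | 0.050 | 0.050 |
| 1 | 0.23 | 0.074 | 0.049 |
| 2 | 0.40 | 0.137 | 0.049 |
| 3 | 0.54 | 0.223 | 0.050 |

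This is deliberately severe: every mover is the worst available case and all go the same way. It also uses a single time point rather than the planned repeated measures.

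**5. Scale against what the trial can detect.** The stated 45 cannot be reproduced, because no effect size or standard deviation is given. Working backwards by the normal approximation, with two-sided alpha assumed at 0.05 and power 0.80, 15 per arm detects a pairwise difference of (1.960 + 0.842) × √(2/15) = 1.02 SD. Two extreme moves would therefore create a spurious difference of about 0.40/1.02 = 39% of that.

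**The case against.** The strongest reply is that the grouping sentence is not an analysis rule. It sits under Eligibility and leads into the names of the three arms. It can be read as a loose way of saying what the arms were. The analysis plan never says patients are analysed as treated, and the design is called randomised. This reading is fair, and it means the documents cannot be said to commit firmly to an as-treated analysis. It does not close the gap, because on this reading no analysis population is defined anywhere. Analysis by randomised arm is unassured either way, and the same sentence repairs both.

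A reader might go further and infer that switching was built into the design: two arms seem to depend on finding a trigger point, and the Eligibility section notes "Local twitch response was not observable in all cases". The documents do not support that inference.
- Every patient had to have at least one masseter trigger point to enrol.
- Localisation also relied on the patient's report of pain and on digital palpation.
- The missing twitch is given no consequence for treatment.
- Known hypersensitivity to local anaesthetic, one obvious reason to depart from assignment, is an exclusion.
- All visits are timed from the injections, and no later phase is described in which patients could cross over.

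No switch or refusal is reported or anticipated.

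The objection that the bias figures are hypothetical also stands. The number of movers and their difference in outcome are assumed, and with no movers the bias is zero.

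**Conclusion.** The point holds as a defect in wording and specification. The only definition of the groups is treatment received, it sits badly with a randomised design, and nothing elsewhere provides for analysis by assigned arm. Followed literally, the comparison is as-treated.

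A reader might conclude that this trial has already lost the protection of randomisation. The documents do not show that. The loss requires both that some patient's received and assigned treatments differed and that the analysis followed receipt. Neither is shown.

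The size is therefore conditional. It is zero with no departures. Each departure moves 6.7% of one arm and makes up 6.25% of another. Under the extreme selective pattern assumed above, one to three departures give a type I error of about 0.07 to 0.22. Departures unrelated to prognosis would do less harm. These figures show only that small arms tolerate few selective moves.

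**What to change.** Replace the grouping sentence under Eligibility with: *Patients are analysed in the arm to which they were randomised, whatever treatment they received.* Keep the list of the three arms, and let the Statistical Analysis Plan use the same definition of group. Report, by arm, how many patients received a technique other than the one assigned, including when the number is zero. Any as-treated analysis should be labelled as sensitivity only.

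The cost is one sentence and one line of reporting. If there were no departures, no result changes. If there were, the estimated contrast may move in either direction, and it will describe the effect of being assigned a technique rather than of receiving it.

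The sentence settles which arm a patient belongs to. It does not settle missing visits. Standard repeated measures ANOVA needs complete data from T0 to T3, so any rule for incomplete follow-up is a separate decision and should not be added here without its own justification.

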**Sample size**

The sample size was calculated using IBM SPSS 22 (IBM SPSS Statistics for Windows, Version 22.0. Armonk, NY: IBM Corp.). Based on a power of 0.80 and an alpha value of 0.05, the sample size was calculated to be a total of 45 subjects with 15 in each group.

**Outcome measures**

The Rate of Pain on Function (PoF) assessed by Numerical pain Scale (NRS): Patients rated their pain on function (pain during chewing or speaking etc.) on a Numeric Rating Scale (NRS) (0–10 where 0 is no pain and 10 is the worst pain imaginable)

The Rate of Pain Intensity on Palpation (PoP): Patients rated their pain intensity on masseter muscle by a 4-point Likert-type scale (0 = no pain, 3 = as worst pain imaginable) while a calibrated examiner palpating their masseter muscle.

The measurement of pain-free maximum mouth opening (MMO) in millimeters.: Pain-free MMO was measured as the distance between the incisal edges of the upper and lower incisors while patient's mouth is open as possible without any assistance and without pain in masseter muscle. Three measurements were performed, and their average is recorded.

The patients were assessed before the injections (T0), and at one week (T1), 4 weeks (T2), and 12 weeks (T3) after the injections. Patient's pain on palpation, pain on function and maximum mouth opening values were reexamined and recorded on follow-up appointments. Treatment protocol and the outcome measures were recorded in the patient's form.

Statistical Analysis Plan: Descriptive statistics of variables were presented as mean  $\pm$  standard deviation for continuous variables and n (%) for categorical variables in statistical analysis. IBM SPSS 22 was used to analyze the data (IBM SPSS Statistics for Windows, Version 22.0. Armonk, NY: IBM Corp.). Pearson chi-square test was used in the analysis of categorical variables. One-way ANOVA was used in the analysis of discontinuous variables (such as % difference Baseline-T1). Bonferroni test was used as post hoc test after ANOVA. Repeated Measures ANOVA test was used when testing group differences for repeated measurements. Bonferroni correction was used in multiple comparisons when determining the differences between the groups at each time point. The statistical significance level was accepted as  $p < 0.05$ .

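### All three outcomes depend on the patient's own report, and the plan describes no patient masking or common information, so differences between arms may partly reflect expectation

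*Combined protocol and SAP*

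**What the plan says.** The Study Design section reads "This is a 3-armed randomized, parallel, controlled, interventional clinical study enrolling 45 patients". It does not mention masking.

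The Eligibility section names the arms as "Masseteric nerve block (MNB), TrP injections with local anesthetic (LA) and dry-needling (DN"). It describes no sham, double-dummy or shared procedure, and no standard wording for patients. It does say that the examiner's palpation was calibrated with a pressure algometer (1.5 Kg).

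The Outcome measures section defines three outcomes:

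- Pain on function (PoF), 0 to 10: "Patients rated their pain on function (pain during chewing or speaking etc.) on a Numeric Rating Scale (NRS").
- Pain on palpation (PoP), 0 to 3: "Patients rated their pain intensity on masseter muscle by a 4-point Likert-type scale", given during palpation by a calibrated examiner.
- Pain-free MMO, in millimetres, the average of three measurements, with the mouth "open as possible without any assistance and without pain in masseter muscle".

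Outcomes are taken at baseline and at 1, 4 and 12 weeks. No expectation rating or treatment-guess question is listed. The Statistical Analysis Plan paragraph tests group differences by ANOVA methods with Bonferroni correction.

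**The concern.** No outcome is independent of the patient. Two are direct ratings. The third is a measured distance, but its end point is the moment the patient would feel pain. A patient who knows the assigned procedure may expect more or less from it, and that expectation can enter all three results.

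Randomisation does not remove this, because the expectation arises from knowing the allocation. Bonferroni correction does not remove it either, because it controls chance error and not bias. If expectation differs between arms, the planned analysis would count that difference as treatment effect and could not separate the two.

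**Working it through.** **1. How each outcome depends on the patient and the examiner**

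| Outcome | What the patient determines | What the examiner can influence |
|---|---|---|
| PoF | the whole score | nothing in the rating as described |
| PoP | the score | the pressure applied |
| MMO | the stopping point | coaching and measurement |

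Patient expectation can reach all three rows. Masking the examiner would close a separate route for PoP and MMO, but would not act on the patient's own expectation.

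**2. The plan's own figure**

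The Sample size section gives 45 patients, 15 per arm, "Based on a power of 0.80 and an alpha value of 0.05". It states no effect size, SD, outcome or test, so 45 cannot be reproduced. The point does not depend on it; 15 per arm is taken as given.

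**3. Illustration of scale**

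Inputs from the documents: n = 15 per arm, three arms, alpha 0.05, Bonferroni comparisons. With three pairs, the per-pair level is 0.05/3 = 0.0167.

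Assumed inputs, because the documents give none: true difference zero; expectation shifts one arm by d = 0.25 or 0.5 SD. At an assumed NRS SD of 2 this is 0.25 × 2 = 0.5 point or 0.5 × 2 = 1 point. One time point; two-sided tests.

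Formula: the pairwise t statistic with pooled variance follows a noncentral t distribution with 3 × 15 − 3 = 42 df and noncentrality d × √(n/2) = d × √7.5 = 2.739d.

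- d = 0.25: noncentrality 0.685
- d = 0.5: noncentrality 1.369
- Critical values: 2.018 at 0.05; 2.494 at 0.0167

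Probability that a pair containing the shifted arm is declared different:

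| Shift | at 0.0167 (Bonferroni) | at 0.05 (unadjusted) |
|---|---|---|
| none | 0.017 | 0.050 |
| 0.25 SD | 0.043 | 0.103 |
| 0.5 SD | 0.142 | 0.267 |

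The excess at the Bonferroni level is 4.3 − 1.7 = 2.6 to 14.2 − 1.7 = 12.5 percentage points. Using only the two arms compared (28 df) gives nearly the same values: 0.042 and 0.137 at 0.0167; 0.101 and 0.262 at 0.05.

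**4. Dependence on the assumed SD**

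For a 1-point shift in one arm at the Bonferroni level (28 df), the probability is 0.254 at SD 1.5, 0.137 at SD 2 and 0.088 at SD 2.5.

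**5. Effect of sample size**

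Because the shift is a bias, more patients make it worse. At 0.5 SD and level 0.05, the probability rises from 0.27 with 15 per arm to 0.48 with 30 and 0.78 with 60.

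**The case against.** The strongest case is that comparing openly delivered procedures is a legitimate pragmatic design. All three arms are active needle procedures, so part of any expectation is shared. What patients were told would normally stand in the consent material, which is not part of the text reviewed. This much stands: the silence of the available sections does not show that patients were told their arm or were told different things.

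Four stronger readings are tempting and are not supported:

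- **That the bias favours the nerve block or the anesthetic injection over dry needling.** The documents give procedure names only. They do not describe what patients feel or expect, so both the difference in sensation and the direction of bias are inferences.
- **That masking the examiner is useless because the patient is the rater.** PoP is rated during palpation by "a calibrated examiner palpating their masseter muscle", and calibration is not masking. An examiner who knows the arm could press differently or coach the opening. Masking remains useful for PoP and MMO.
- **That up to 27% of comparisons would be false positives.** That figure is for unadjusted tests, whereas the plan specifies Bonferroni. The shift itself is assumed, and nothing shows whether it would persist to 4 or 12 weeks.
- **That adjusting for an expectation rating would solve the problem.** In contrasts with the nerve block, where the arm is known, a rating taken after allocation may itself be affected by it. In a masked pair, a rating before the procedure misses expectation that arises if the patient later recognises the treatment. A treatment guess at week 1 can reflect relief already felt.

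The sections are also written in the past tense, which suggests that treatment may be complete. If so, design changes are no longer possible.

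The objection does not remove the core of the point: every outcome is determined by the patient, and the plan states no safeguard against unequal expectation.

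**Conclusion.** The concern holds in limited form. PoF and PoP are patient-rated, pain-free MMO stops at the patient's pain, and the available text describes no patient masking and no common information. A difference between arms may therefore partly reflect expectation. That it does so, by how much and in whose favour cannot be determined from the documents.

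Under the stated assumptions, the chance of a false pairwise finding at the plan's Bonferroni level would be about 2.6 to 8.5 times the nominal value (0.043/0.0167 to 0.142/0.0167). This illustrates scale and is not an estimate for this trial. The absence of safeguards is judged on the available sections only. The point should be addressed, since at least part of the remedy is cheap.

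**What to change.** **In the Eligibility section, where the arms are described**, state that:

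1. all arms receive one identical, neutral script saying that it is not known which procedure is better;
2. patients in the two trigger-point arms (LA and DN) are not told which they receive, with instruments out of sight and the same preparation and contact time.

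**In the Outcome measures section and the Statistical Analysis Plan paragraph**, state:

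3. who is masked: patient, operator, examiner. Masking the examiner is worth having for PoP and MMO;
4. that contrasts with MNB are unmasked for these patient-determined outcomes, and that conclusions from them are limited to a treatment effect that includes expectation.

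A 0 to 10 rating of expected relief just before the procedure may be recorded as descriptive information. It should not be presented as an adjustment that removes the bias.

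**Cost:** a one-page script, a few sentences of text and, if wanted, one item on the existing patient form. The script and concealment need no extra staff or visits. Masking of LA against DN will be partial, because numbness may reveal the anesthetic, and consent wording must cover not naming the procedure. If treatment is already complete, only the statement of who was masked and the limited conclusions apply.

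### Tying the self-rated pain-on-function score to follow-up appointments, with no other route described, creates a risk of avoidable, possibly outcome-related, missing data at T1 to T3

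*Combined protocol and SAP*

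**What the plan says.** The follow-up schedule is in the Outcome measures section: "The patients were assessed before the injections (T0), and at one week (T1), 4 weeks (T2), and 12 weeks (T3) after the injections". The collection rule follows it: "Patient's pain on palpation, pain on function and maximum mouth opening values were reexamined and recorded on follow-up appointments".

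The three outcomes differ in what they need:

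- **PoF:** "Patients rated their pain on function (pain during chewing or speaking etc.) on a Numeric Rating Scale (NRS"), scored 0 to 10. No examiner step is described.
- **Pain on palpation (PoP):** rated by the patient, but "while a calibrated examiner palpating their masseter muscle".
- **Maximum mouth opening (MMO):** a distance in millimetres; "Three measurements were performed, and their average is recorded".

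The Sample size section states that "the sample size was calculated to be a total of 45 subjects with 15 in each group" and gives no allowance for dropout. The Statistical Analysis Plan paragraph names repeated measures ANOVA for the repeated outcomes and Bonferroni correction for group comparisons at each time point. The documents do not say what happens when a patient misses a visit. They state no missing-data method and no analysis population, and they name no primary outcome.

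**The concern.** PoP and MMO cannot be obtained without a visit. PoF can, because one question by telephone or message supplies it. As the rule stands, a patient who feels well at week 4 and does not return, or who is still in pain and seeks care elsewhere, leaves no PoF score at that visit or later.

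Two things are at stake. The first is precision: with 15 patients per arm and no dropout allowance, a few absences matter. The second is bias: willingness to return may depend on how well the treatment worked, and that dependence may differ between arms. The 12-week PoF comparison would then describe attenders only. A model or an imputation can replace unasked scores only with assumptions. The point here is therefore which data are obtained, which is separate from how gaps are analysed afterwards.

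**Working it through.** **The plan's own figure.** The total of 45 rests on "Based on a power of 0.80 and an alpha value of 0.05" and on nothing else that is stated: no effect size, SD, outcome or dropout rate. It cannot be reproduced forwards. Solved backwards at 80% power and alpha 0.05, 45 patients in three arms correspond to Cohen's f = 0.48 for the omnibus F test. For one pair of arms by two-sided t test, they correspond to a standardised difference of 1.06.

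**Inputs for the illustration**

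- From the documents: 15 per arm; alpha 0.05; Bonferroni correction, taken as 0.05/3 for three pairs.
- Assumed: SD 2 and true difference 2 NRS points, so d = 2/2 = 1.0; two-sided tests; 3 of 15 absent per arm (4 of 15 as a variant); absentees 2 points worse than attenders (range 1 to 3).

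**Precision.** The standard error of a difference is SD × √(2/n).

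- n = 15: 2 × √(2/15) = 0.730
- n = 12: 2 × √(2/12) = 0.816
- Ratio: √(15/12) = 1.118, a rise of 12%

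Power comes from the noncentral t distribution with noncentrality d × √(n/2) and 2n − 2 degrees of freedom:

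| n per arm | Noncentrality | df | Power at 0.05 | Power at 0.05/3 |
|---|---|---|---|---|
| 15 | 2.739 | 28 | 0.75 | 0.58 |
| 12 | 2.449 | 22 | 0.65 | 0.46 |
| 11 | 2.345 | 20 | 0.61 | 0.41 |

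Power starts at 0.75, not 0.80, because the assumed d of 1.0 is a little below the 1.06 that 15 per arm would detect with 80% power.

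**How much remote collection could recover.** Take the omnibus test at f = 0.48 and an assumed 20% loss.

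- No recovery: 45 × 0.80 = 36 scores, power 69%.
- Half of the lost scores recovered: 45 × (1 − 0.20 × 0.5) = 40.5 scores on average, power 75%.
- All recovered: 45 scores, power 80%.

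Recovering half of the lost scores therefore gains about 6 percentage points.

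**Bias.** Let p be the share of an arm that is absent and D the mean of absentees minus the mean of attenders. The attenders' mean differs from the full-arm mean by −pD. The error in the difference A − B is therefore p_B·D_B − p_A·D_A.

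- Equal loss and equal gap (3/15 in both arms, D = 2 in both): 0.4 − 0.4 = 0. Each arm mean is off by 0.4, but the comparison is unbiased.
- 3/15 absent in one arm with D = 2, and absence unrelated to pain in the other (D = 0): the error is (3/15) × 2 = 0.4 points in size, or 0.4/2 = 20% of the assumed difference.
- Unequal loss, 1/15 against 4/15, D = 2 in both: (4/15 − 1/15) × 2 = 0.4 points. With D = 1 or 3 it is 0.2 or 0.6.

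**Link to the analysis.** A classical repeated measures ANOVA normally drops any patient with a missing visit. If 10% missed each of three visits independently (an assumption), 0.9³ = 0.729 of patients would be complete, about 33 of 45. For the same reason, recovering one PoF score helps only if that patient's other visits are complete or the model accepts incomplete series.

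**The case against.** Three visits over 12 weeks is a light schedule, and PoP and MMO need the visit in any case. Recording all three outcomes together under the same conditions is a legitimate design. Nothing in the plan is contradictory or invalid on this point. The larger gap is arguably that no missing-data method, analysis population or dropout allowance is stated. With no primary outcome named, giving PoF priority is a reviewer's choice. Patients who have left for care elsewhere may not answer a call either.

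Most of this stands, and it limits the point to an inexpensive improvement. It does not remove the point: PoF is the one outcome for which the loss can be prevented, and better analysis cannot supply scores that were never requested.

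A reader might infer that the plan does add outcome-related missing data, or that the 12-week comparison is biased. The documents do not support either reading. They report no missed visit and no reason for absence, and equal loss with an equal gap leaves the arm difference unbiased. Nor do they say that appointments are the only route; that follows from the absence of any other. The power figures above are the total loss from absence, not the part that a telephone call would restore.

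The text is also largely in the past tense. If follow-up is complete, the collection rule can no longer be changed.

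**Conclusion.** The concern holds as a risk. The described collection rule ties a self-rated score to attendance without need, and so exposes PoF at T1 to T3 to loss that is avoidable and possibly related to outcome. The actual size is unknown.

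Under the stated assumptions, an absence of 3 in 15 per arm costs about 10 percentage points of pairwise power at 0.05 and about 12 at the Bonferroni level, of which remote collection would recover only a part. A bias of 0.4 points requires a loss or a gap that differs between arms. The SD, true difference, absence rates and absentee gap are all illustrative, since the documents give none of them. The change is worth making because it is cheap and the arms are small.

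**What to change.** For follow-up not yet completed, add to the follow-up paragraph of the Outcome measures section: if a patient misses or declines T1, T2 or T3, obtain the PoF score by telephone or message at the scheduled time, with the same wording and scale. Record the reason for absence (pain resolved, persisting pain, other treatment, adverse effect, unrelated) and the mode of collection. PoP and MMO stay visit-only.

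In the Statistical Analysis Plan, analyse these scores in the randomised arm with a model that keeps patients with incomplete visits, such as a mixed model for repeated measures. Add a sensitivity analysis that excludes the remotely collected scores.

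If collection is already complete, report attendance and any known reasons for absence by arm and visit, and make the analysis change alone.

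The cost is a few sentences and an occasional call by existing clinic staff. The downside is that a few PoF scores would be collected by a different mode, which the flag and the sensitivity analysis address.
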